9.9.5.5. Discount Power Prior Extension of the t-test

Taking the outcome as BP change from baseline, we can apply a t-test to determine the treatment effect between arms. Generalizing the Bayesian discount power approach to this model is described in section 2.5 of Haddad et al [2]. This model does not adjust for baseline BP, so the issue of mean centering is redundant. This analysis will be performed using the 'bdpnormal()' function, in version 1.3.2. of the bayesDP package, available on the Comprehensive R Archive Network (CRAN) [<https://CRAN.R-project.org/>].

9.9.6. Secondary Analysis of Primary Efficacy Endpoint

As a secondary analysis of the powered primary efficacy endpoints, frequentist ANCOVA methods will be used to determine the baseline adjusted treatment effect for the study populations defined in section 9.1.3.

As outlined in section 9.8, the first and second interim analyses takes place when a minimum of 110 and 149 subjects have 6-month follow-up ABPM data available respectively. At each interim analysis, the Bayesian efficacy analysis will be performed and, if the pre-specified stopping rules are met, then enrollment will be stopped. If the study stops for efficacy or futility at either the first or second interim analysis, then any additional subjects that have been enrolled before the decision to stop has been made will not be part of the primary endpoint analysis, but instead will be pooled with the existing subjects and analyzed as a secondary cohort. This analysis will be performed using frequentist ANCOVA methods to determine the baseline adjusted treatment effect and will be performed by Medtronic, as Medtronic will be unblinded at this stage.

9.9.7. Secondary Efficacy Objectives

The following additional secondary efficacy endpoints will be assessed:

- Change in SBP from baseline (SV2) as measured by 24-hour ABPM at 3, 6, 12, 24 and 36 months post-procedure.
- Change in office SBP from baseline (SV2) at 1, 3, 6, 12, 24 and 36 months post-procedure.
- Change in DBP from baseline (SV2) as measured by 24-hour ABPM at 3, 6, 12, 24 and 36 months post-procedure.
- Change in office DBP from baseline (SV2) at 1, 3, 6, 12, 24 and 36 months post-procedure.

- Incidence of achieving target office SBP (SBP <140 mmHg) at 1, 3, 6, 12, 24 and 36 months post-procedure.

RDN vs. control groups will be compared out to 6-months post randomization, prior to the crossover procedure. Statistical comparisons will be performed using the independent samples t-test for continuous endpoints and Fisher's exact test for categorical endpoints. In addition, two-sided 95% confidence intervals of the difference between RDN and control groups will be presented. Changes in blood pressure measurements from baseline to follow-up within each treatment group will be assessed using paired t-tests. Two-sided 95% confidence intervals of the mean change from baseline will be presented for each treatment group. analysis of covariance (ANCOVA) models, adjusting the treatment effect for the baseline BP measurements will also be applied to all continuous secondary endpoints.

RDN vs. crossover vs. non-crossover groups will be compared out to 36 months post-procedure using chi-square tests for categorical data and ANOVA for continuous data.

Changes in blood pressure measurements from baseline to follow-up within each group will be assessed using paired t-tests. Two-sided 95% confidence intervals of the mean change from baseline will also be presented for each group.

The secondary efficacy analyses will be presented for all the study populations defined in section 9.1.3.

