The objective of this study is to test the hypothesis that renal denervation is safe and reduces systolic blood pressure (SBP) in patients with uncontrolled hypertension on one, two, or three standard antihypertensive medications compared to a sham-controlled population. In this study, "uncontrolled hypertension" is defined as an office systolic blood pressure (SBP) ≥ 150 mmHg and < 180 mmHg, an office Diastolic Blood Pressure (DBP) ≥ 90 mmHg and a 24-hour Ambulatory Blood Pressure Monitoring (ABPM) average SBP ≥ 140 mmHg to < 170 mmHg, all of which are measured at screening visit 2. Data obtained will be used to confirm the effect of renal denervation on elevated blood pressure in patients on 1, 2 or 3 anti-hypertensive medications. Data collected during the SPYRAL HTN-ON MED trial may be used to gain market approval or additional indications for the Symplicity Spyral™ multi-electrode renal denervation catheter (Symplicity Spyral™ catheter) and the Symplicity G3™ renal denervation RF generator from regulatory entities, including, but not limited to: the Pharmaceuticals and Medical Device Agency (PMDA), Health Canada, and the U.S. Food and Drug Administration (FDA).

5. Study Endpoints

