The prior data consists of the first consecutively randomized 80 subjects in the SPYRAL HTN-ON MED study, which were randomized in a 1:1 ratio to RDN or control. The results from these 80 subjects have already been analyzed and published [6].

The prospective data consists of the following two cohorts:

[figure not shown]
1. Subjects 81 to 106 which have already been enrolled and were randomized in a 1:1 ratio to RDN vs. control, and whose data has not been unblinded and analyzed by Medtronic.
2. All remaining subjects in the SPYRAL HTN-ON MED Study from 107 onwards which will be randomized in a 2:1 ratio to RDN vs control.

The weight of the prior data will be adjusted using a discount function, which scales from 0 to 1, according to the similarity of the prior and prospective data. The discount function adjusts the amount of weight the prior receives. This prevents the use of an informative prior where exchangeability issues are present (e.g., the prior and prospective data are quite different). This discount function approach was proposed by the Medical Device Innovative Consortium (MDIC) working group and is a collaborative

effort between FDA and industry through the MDIC [1,2]. If the analyses show a high level of agreement for prospective data compared to the prior, the prior will be weighted at or near 100%. If the prospective data perform much worse than or much better than the prior, then the prior will receive very little or zero weight. The Bayesian adaptive design is set up to enroll patients until a sufficient sample size is achieved to have high probability of meeting the endpoint.

The sample size of the study will vary from a minimum of 110 to 221 subjects with evaluable data due to the adaptive nature of the trial. This will require approximately 130 to 260 randomized subjects assuming a 15% rate of attrition at 6-months.

- The first interim analysis will take place when we have a minimum of 110 subjects with evaluable data. With an expected attrition rate of 15%, this will require approximately 130 randomized subjects. If the attrition rate is higher than 15%, then additional subjects will be randomized in order to reach a minimum of 110 evaluable subjects.

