9.2. General Methodology

Descriptive statistics of continuous outcomes will be presented by treatment group and include sample size, mean, median, standard deviation, minimum and maximum. For categorical outcomes, the number and percentage of subjects in each category will be presented by treatment group. Statistical comparisons between treatment groups will be made using the independent samples t-test for continuous outcomes and Fisher's exact test for categorical outcomes. Paired t-tests will be used to compare changes in blood pressure from baseline to follow-up within each treatment group. All statistical analyses will be performed using SAS for Windows (version 9.2 or higher) or other widely accepted statistical or graphical software. Patient data listings and tabular and graphical presentations of results will be provided. Unless otherwise specified, a two-sided 0.05 level of significance will be used to declare treatment groups significantly different.

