9.9.8. Additional Objectives

- Quality of Life (QOL) EQ-5D measures.
- Antihypertensive medication usage throughout the study, including escape patients and subjects with medication changes within 6-month follow-up.
- Additional procedural characteristics e.g. treatment duration, frequency of distal renal artery treatment, ablations per vessel, location of ablations, number of ablations per patient and other characteristics will be analyzed to assess their impact on blood pressure.
- Medication adherence will be assessed using results from drug testing, witnessed pill intake and BP protocol deviations. In addition, we will perform analyses to evaluate the effect of medication adherence on blood pressure change.
- Analyses looking at long term imaging will be performed.

RDN vs. control groups will be compared out to 6-months post randomization, prior to the crossover procedure. Statistical comparisons will be performed using the independent samples t-test for continuous endpoints and Fisher's exact test for categorical endpoints. In addition, two-sided 95% confidence intervals of the difference between RDN and control groups will be presented.

RDN vs. crossover vs. non-crossover groups will be compared out to 36 months post-procedure using chi-square tests for categorical data and ANOVA for continuous data.

Changes in continuous measurements from baseline to follow-up within each group will be assessed using paired t-tests. Two-sided 95% confidence intervals of the mean change from baseline will also be presented for each group.

The additional objectives will be analyzed using the ITT study population defined in section 9.1.3.1.

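### The binary target endpoint (office SBP <140 mmHg) is compared to 6 months only by an unadjusted Fisher's exact test, although baseline office SBP sets how far each subject must fall: a valid test, with a modest loss of efficiency

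*SAP*

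**What the plan says.** Section 9.9.7 lists one binary secondary efficacy endpoint: "Incidence of achieving target office SBP (SBP <140 mmHg) at 1, 3, 6, 12, 24 and 36 months post-procedure". For RDN against control to 6 months it prescribes an independent-samples t-test for continuous endpoints and Fisher's "exact test for categorical endpoints", with 95% CIs for the between-group difference. It then adds ANCOVA, "adjusting the treatment effect for the baseline BP measurements will also be applied to all continuous secondary endpoints". That sentence does not reach the binary endpoint, and no other section gives it a baseline-adjusted comparison. Section 9.11 uses baseline office SBP only as a subgroup factor.

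After 6 months the three groups formed by crossover are "compared out to 36 months post-procedure using chi-square tests for categorical data and ANOVA for continuous data". Fisher's test, and this point, therefore concern the visits to 6 months only.

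Section 4 sets entry at "an office systolic blood pressure (SBP) ≥ 150 mmHg and < 180 mmHg" at screening visit 2 (SV2). Section 7 stratifies randomization by study center only, so baseline pressure is not balanced by design. Under section 9.2, unless otherwise specified, "a two-sided 0.05 level of significance will be used to declare treatment groups significantly different".

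**The concern.** A subject who enters at 150 mmHg reaches the target with a fall of just over 10 mmHg; one who enters just under 180 mmHg needs about 40 mmHg. Baseline office SBP is therefore part of what decides the outcome, and it is already recorded for everyone. The plan uses it when the same measurement is analysed as a change, and leaves it out once that measurement is cut at 140 mmHg. What is at stake is precision: some avoidable noise stays in the comparison, and an exact test on a modest number of responders runs below its nominal level. The validity of the result is not in question.

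**Working it through.** The SAP states no power, response rate or SD for this endpoint, so there is no planned figure to reproduce. The check is a simulation.

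**Inputs from the SAP.** Two-sided level 0.05 (9.2). Baseline range 150 to <180 mmHg (section 4). Subjects 81 to 106 at 1:1, then "from 107 onwards which will be randomized in a 2:1 ratio to RDN vs control" (section 8). About 130 randomized at the first look, 260 at most, 15% attrition (section 8).

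- At 260: RDN 13 + (2/3)(234) = 169 and control 13 + (1/3)(234) = 91. Times 0.85: 143.7 and 77.4, so 144/77 (221 in all, the SAP's own number).
- At 130: RDN 13 + (2/3)(104) = 82.3 and control 13 + (1/3)(104) = 47.7. Times 0.85: 70.0 and 40.5, so 70/41.

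**Inputs assumed.** Baseline office SBP normal, mean 163, SD 8, truncated to 150–180. Residual SD 12 or 15. Mean control change −2.5 or −8 mmHg. Treatment effect 0, −5 or −7 mmHg. Slope of change on baseline 0 or −0.4. Table 3 of the SAP gives −5 mmHg and SD 12, but for 24-hour SBP; they serve here only as stand-ins. The arms are the prospective subjects.

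**How strongly baseline acts.** For a control subject with baseline x, P(response) = Φ{[140 − x − m − s(x − 163)]/σ}, with mean change m, slope s and residual SD σ. With m = −8 and σ = 12:

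- s = 0: x = 150 gives Φ(−2/12) = 0.43; x = 163 gives Φ(−15/12) = 0.11; x = 179 gives Φ(−31/12) = 0.005.
- s = −0.4: x = 150 gives Φ(−7.2/12) = 0.27; x = 179 gives Φ(−24.6/12) = 0.02.

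Baseline is prognostic either way, less so when higher values fall further.

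**Tests compared** (4,000 trials per row of the table):

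1. Fisher's exact test.
2. Pearson without correction: z = (pR − pC)/√[p(1 − p)(1/nR + 1/nC)].
3. Adjusted score test: fit logit P(Y = 1) = a + bx without treatment; take U = Σ t(y − p̂) and its variance V given a and b; reject if U²/V > 3.84.

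Pearson minus Fisher approximates the cost of the exact test; adjusted score minus Pearson approximates the value of the covariate. The runs with the extremes of each difference are included below (differences in points).

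| N | Effect | SD | Control change | Slope | Fisher | Pearson | Adj. score | Total gain | Exact-test part | Covariate part |
|---|---|---|---|---|---|---|---|---|---|---|
| 221 | −5 | 12 | −2.5 | 0 | 0.222 | 0.266 | 0.297 | 7.5 | 4.4 | 3.1 |
| 221 | −7 | 12 | −2.5 | 0 | 0.475 | 0.521 | 0.570 | 9.5 | 4.6 | 4.9 |
| 221 | −5 | 12 | −8 | 0 | 0.361 | 0.381 | 0.438 | 7.7 | 2.0 | 5.7 |
| 221 | −7 | 12 | −8 | 0 | 0.667 | 0.686 | 0.744 | 7.7 | 1.9 | 5.8 |
| 221 | −5 | 15 | −2.5 | 0 | 0.218 | 0.246 | 0.266 | 4.8 | 2.8 | 2.0 |
| 221 | −7 | 15 | −2.5 | 0 | 0.427 | 0.463 | 0.500 | 7.3 | 3.6 | 3.7 |
| 111 | −7 | 15 | −2.5 | 0 | 0.233 | 0.246 | 0.278 | 4.5 | 1.3 | 3.2 |
| 111 | −7 | 12 | −2.5 | −0.4 | 0.218 | 0.287 | 0.302 | 8.4 | 6.9 | 1.5 |
| 111 | −5 | 15 | −8 | −0.4 | 0.172 | 0.196 | 0.206 | 3.4 | 2.4 | 1.0 |
| 111 | −7 | 15 | −8 | −0.4 | 0.321 | 0.368 | 0.371 | 5.0 | 4.7 | 0.3 |

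Separate runs of 3,000 trials covered slope −0.4 at 144/77 with SD 12. Fisher to adjusted score went from 0.21 to 0.29 and 0.48 to 0.56 (control change −2.5, effects −5 and −7), and from 0.46 to 0.50 and 0.76 to 0.80 (control change −10).

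**Size under no effect.** Fisher 0.025–0.039; Pearson 0.033–0.057; adjusted score 0.043–0.057, with further runs up to 0.060. An adjusted likelihood-ratio test gave 0.053–0.063 at N = 221 and up to 0.084 at N = 111 when only 5–6% responded, which is why the score test is the one to name.

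**Precision.** The Monte Carlo standard error of one power figure is at most √(0.25/4000) = 0.8 points. The smallest covariate gain, 0.3 points, is a net 12 trials in 4,000, in effect nothing. Because Pearson's own size is not exactly 0.05, the split is approximate.

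**The case against.** The best case for the plan is that nothing here is wrong. Fisher's test is valid under randomization, pre-specified, and used in the same way in sections 9.2, 9.9.7 and 9.9.8. The ANCOVA sentence is limited to continuous endpoints, so the text does not contradict itself. Change in office SBP at the same visits already gets a baseline-adjusted analysis, so a reader worried about imbalance has an adjusted result on the underlying measure. Chance imbalance is in any case allowed for in the test's error rate. Study success depends only on the two primary endpoints. All of this stands, and it limits the weight of the point.

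Three stronger readings are tempting and should not be drawn.

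- **That power is lost for no benefit.** Fisher keeps the error rate below 5% with few responders and needs no model; the likelihood-ratio results above show what an adjusted test can do in sparse data.
- **That the whole loss comes from omitting baseline.** Between 1.3 and 6.9 points of it is the conservatism of the exact test, and the covariate's share can shrink to almost nothing when change depends on baseline.
- **That EQ-5D in section 9.9.8 has the same fault.** It is an additional objective, which section 9.9.2 asks to have summarized, and the distance-to-target argument does not apply to it. No calculation here bears on it.

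What survives is narrower. Dichotomizing office SBP does not remove its dependence on baseline, and the plan gives no reason for adjusting one form of the measurement and not the other.

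**Conclusion.** The point holds as a minor efficiency gap. To 6 months, the only binary secondary efficacy endpoint has no baseline-adjusted analysis, although its baseline value sets each subject's distance to the target. Adding the adjustment and moving from the exact test to a score test gains about 3 to 10 points of power, of which about 0.3 to 6 belong to the covariate. The direction was the same in every non-null scenario tried. The size depends on office SBP inputs that the SAP does not supply, above all the slope of change on baseline, and at slope −0.4 the covariate's share is at the low end. No success criterion and no power statement is affected.

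**What to change.** Extend the ANCOVA sentence in section 9.9.7 to say that office SBP <140 mmHg at visits to 6 months will also be analysed by logistic regression on treatment and SV2 office SBP. State that treatment is tested by the score test, and that the standardized risk difference is reported with its 95% CI. This difference averages the model's predictions over all subjects under each arm, so it targets the same marginal quantity as the unadjusted comparison.

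Keep Fisher's exact test and report both. Do not switch between them according to the number of responders; a data-dependent choice of test is unnecessary when both are shown. The score test and the interval need not agree exactly at the margin, so the text should say that the risk difference is the effect estimate.

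The cost is a sentence or two of SAP text and a few lines of code. No new data are needed, and no other analysis changes.

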9.9.8. Additional Objectives

- Quality of Life (QOL) EQ-5D measures.
- Antihypertensive medication usage throughout the study, including escape patients and subjects with medication changes within 6-month follow-up.
- Additional procedural characteristics e.g. treatment duration, frequency of distal renal artery treatment, ablations per vessel, location of ablations, number of ablations per patient and other characteristics will be analyzed to assess their impact on blood pressure.
- Medication adherence will be assessed using results from drug testing, witnessed pill intake and BP protocol deviations. In addition, we will perform analyses to evaluate the effect of medication adherence on blood pressure change.
- Analyses looking at long term imaging will be performed.

RDN vs. control groups will be compared out to 6-months post randomization, prior to the crossover procedure. Statistical comparisons will be performed using the independent samples t-test for continuous endpoints and Fisher's exact test for categorical endpoints. In addition, two-sided 95% confidence intervals of the difference between RDN and control groups will be presented.

RDN vs. crossover vs. non-crossover groups will be compared out to 36 months post-procedure using chi-square tests for categorical data and ANOVA for continuous data.

Changes in continuous measurements from baseline to follow-up within each group will be assessed using paired t-tests. Two-sided 95% confidence intervals of the mean change from baseline will also be presented for each group.

The additional objectives will be analyzed using the ITT study population defined in section 9.1.3.1.

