9.7. Treatment Characteristics

Renal denervation treatment measures such as number of ablation attempts and number of generator codes will be summarized separately for each kidney, and for combined kidneys. Anti-hypertensive medication use will also be summarized at baseline and at each follow-up.

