9.9.2. Secondary Safety Objectives

The following secondary safety endpoints will be assessed:

- Acute/Procedural Safety Secondary Endpoints – Compared Between Groups at 1 Month Post-Procedure
 - Significant embolic event resulting in end-organ damage
 - Renal artery perforation requiring intervention
 - Renal artery dissection requiring intervention
 - Vascular complications
 - End-stage renal disease (ESRD)
 - $\geq 40\%$ decline in eGFR
 - Increase in serum creatinine $>50\%$ from screening visit 2
 - New myocardial infarction
 - New stroke
 - Renal artery re-intervention
 - Major bleeding according to TIMI definition (i.e. intracranial hemorrhage, $\geq 5\text{g/dl}$ decrease in hemoglobin concentration, a $\geq 15\%$ absolute decrease in hematocrit, or death due to bleeding within 7 days of the procedure)
 - New renal artery stenosis $>70\%$
 - Hospitalization for hypertensive crisis not related to confirmed non-adherence with medication and/or protocol
- Chronic Safety Secondary Endpoints - Compared Between Groups at 3, 6, 12, 24, and 36 months post-randomization.
 - Composite Safety Endpoint, defined as a composite of the following events:
 - All-cause mortality
 - End-stage renal disease (ESRD)
 - Significant embolic event resulting in end-organ damage
 - Renal artery perforation requiring intervention
 - Renal artery dissection requiring intervention
 - Vascular complications
 - Hospitalization for hypertensive crisis not related to confirmed non-adherence with medications and/or the protocol
 - New renal artery stenosis $>70\%$

- $\geq 40\%$ decline in eGFR
- Increase in serum creatinine $>50\%$ from screening visit 2
- New myocardial infarction
- New stroke
- Renal artery re-intervention
- Major bleeding according to TIMI definition (i.e. intracranial hemorrhage, $\geq 5\text{g/dl}$ decrease in hemoglobin concentration, a $\geq 15\%$ absolute decrease in hematocrit, or death due to bleeding within 7 days of the procedure)
- Hospitalization for hypertensive crisis not related to confirmed non-adherence with medication and/or protocol
- Summary of Health-related Quality of Life (HRQoL) analysis based on reporting measures using accepted QoL instruments (EQ5D)

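### Free improvement: section 9.9.8 compares EQ-5D and continuous medication measures between arms by t-test alone, although their baselines are collected and an ANCOVA on the measure's own baseline would be more precise

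*SAP*

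**What the plan says.** SAP section 9.9.8 lists among its objectives "Quality of Life (QOL) EQ-5D measures" and "Antihypertensive medication usage throughout the study, including escape patients and subjects with medication changes within 6-month follow-up". For RDN against control to 6 months it states: "Statistical comparisons will be performed using the independent samples t-test for continuous endpoints", and it gives Fisher's exact test to the categorical ones. It adds 95% confidence intervals for the difference. It does not say whether the t-test is on the follow-up value or on the change from baseline.

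The baseline enters 9.9.8 only within groups: "Changes in continuous measurements from baseline to follow-up within each group will be assessed using paired t-tests". That implies a baseline EQ-5D. For medication the baseline is explicit. Section 9.7 says "Anti-hypertensive medication use will also be summarized at baseline and at each follow-up", and section 9.9.9 computes the medication burden index at screening visit 2 and at 6 months.

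Section 9.9.7 names the same two tests for the secondary efficacy endpoints, then adds an ANCOVA, "adjusting the treatment effect for the baseline BP measurements will also be applied to all continuous secondary endpoints". Section 9.9.8 has no such sentence.

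**The concern.** A baseline measurement of the same quantity usually predicts its follow-up value better than any other covariate. If it has been collected and is left out of the between-arm comparison, the confidence interval is wider than it need be, and chance imbalance at baseline is handled less well. The SAP accepts this reasoning for blood pressure, where it adjusts for baseline, but does not carry it over to EQ-5D or to continuous medication measures.

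Control subjects may cross over after the 6-month visit (section 9.1.4). The comparison up to 6 months is therefore the only blinded, sham-controlled one for quality of life and drug use, and it cannot be sharpened later with longer follow-up. What is at stake is the precision of these descriptive comparisons. Their validity and the study's success criteria are not in question.

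**Working it through.** **Which ANCOVA clauses exist.** Sections 9.9.3 and 9.9.4 (primary endpoint), 9.9.5 (its sensitivity analyses), 9.9.6 (frequentist analysis) and 9.9.7 (secondary efficacy) all specify or use ANCOVA, and in each the baseline covariate is blood pressure. None uses baseline EQ-5D or baseline medication.

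**The plan's own figure.** The SAP states no SD, correlation, power or sample size for EQ-5D or medication use, so there is nothing to reproduce for this point. The evaluable number used below does reproduce: 260 × 0.85 = 221.

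**Variances.** Let ρ be the correlation between baseline and follow-up, with equal SDs at both times. In units of the follow-up variance, the between-arm difference has variance proportional to:

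- t-test on follow-up values: 1
- t-test on change: 2(1 − ρ)
- ANCOVA on own baseline: 1 − ρ²

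The ratio of ANCOVA to the follow-up t-test is therefore 1 − ρ². Against the change t-test it is (1 − ρ²)/[2(1 − ρ)] = (1 + ρ)/2. The reduction in standard error is 1 minus the square root of the ratio. ρ is an assumption.

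| ρ | variance ratio, vs follow-up | SE reduction | variance ratio, vs change | SE reduction |
|---|---|---|---|---|
| 0.3 | 0.91 | 5% | 0.65 | 19% |
| 0.5 | 0.75 | 13% | 0.75 | 13% |
| 0.7 | 0.51 | 29% | 0.85 | 8% |
| 0.8 | 0.36 | 40% | 0.90 | 5% |

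A simulation of 3,000 trials with 144 and 77 subjects gave ratios of 0.91, 0.77 and 0.51 against follow-up values and 0.65, 0.73 and 0.85 against change, for ρ of 0.3, 0.5 and 0.7. This agrees with the table.

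**What that means at this trial's size.** Assume that the maximum of 260 are the prospective subjects of section 8, with 26 randomized 1:1 and 234 randomized 2:1. RDN has 13 + 156 = 169 and control 13 + 78 = 91. With 15% attrition in each arm, 143.65 and 77.35 are evaluable, about 144 and 77. At two-sided 0.05 (section 9.2) and 80% power, the detectable difference in SD units is

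(1.960 + 0.842) × √v × √(1/143.65 + 1/77.35).

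With v = 1 this is 0.395. At ρ = 0.5, where both t-tests have v = 1 and ANCOVA has v = 0.75, it falls to 0.342. Power for an assumed difference of 0.3 SD rises from 57% to 69%.

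**The case against.** The best defence is that the t-test with a confidence interval is valid and simple, and that these are unpowered additional objectives bearing on neither primary hypothesis. That stands, and it sets the ceiling on the point's importance.

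A second objection concerns size. If the t-test is on change, the baseline is already used, and the gain shrinks as ρ rises: at ρ = 0.9 the ratio is (1 + 0.9)/2 = 0.95 and the standard error falls by only about 2.5%. The number of drugs at baseline may well predict the number at 6 months that strongly. This also stands. The larger gains apply only if follow-up values are tested, which section 9.9.8 leaves open.

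Three stronger readings are tempting, and the SAP does not support them:

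- **That 9.9.7 holds the only ANCOVA clause, with the wrong covariate.** ANCOVA also appears in 9.9.3 to 9.9.6. Every continuous endpoint listed in 9.9.7 is a blood pressure change, so baseline blood pressure is the right covariate there.
- **That medication is compared only by t-test.** Categorical medication measures go to Fisher's exact test, and change in medication burden is the second tier of the win ratio in 9.9.9. That tier is reached only by pairs not decided on 24-hour SBP, so it gives no separate estimate of the medication difference.
- **That EQ-5D is assigned two conflicting tests.** Section 9.9.2 does list "Summary of Health-related Quality of Life (HRQoL) analysis based on reporting measures using accepted QoL instruments (EQ5D") under secondary safety and then names Fisher's exact test. But the item is worded as a summary, and the Fisher sentence follows an algorithm for adjudicated event rates. Sections 9.2 and 9.9.8 both give continuous measures a t-test. This is a duplicate listing at most.

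**Conclusion.** The point holds as a free improvement. Section 9.9.8 has no baseline-adjusted comparison for its continuous measures, the baselines are collected, and the parallel section for blood pressure has such an analysis. Nothing is invalid as it stands, and the primary conclusions do not change.

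The gain in standard error depends on two things that the SAP does not give: the correlation, and whether the t-test is on change or on follow-up values. Over the assumed range of 0.3 to 0.8 it is between 5% and 19% in one case and between 5% and 40% in the other. The figures assume equal SDs at baseline and follow-up; the detectable difference and power also assume the arm sizes derived above.

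**What to change.** Add one sentence to section 9.9.8, following the pattern of 9.9.7: for continuous measures (EQ-5D scores, medication burden), the RDN minus control difference at visits to 6 months will also be estimated by ANCOVA with treatment and the baseline value of the same measure, and this will be the main estimate for those measures. The t-test stays alongside it. Categorical medication measures stay with Fisher's exact test.

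The ANCOVA treatment estimate is the same whether the outcome is entered as change or as follow-up value, so the main estimate would no longer depend on the choice that 9.9.8 leaves open.

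The cost is SAP wording and a small amount of programming. No new data are needed.
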